## **Section L: Cost/Payment**

Delineate clinical procedures from research procedures. Will subject's insurance (or subject) be responsible for research related costs? If so state for which items subject's insurance (or subject) will be responsible (surgery, device, drugs, etc). If appropriate, discuss the availability of financial counseling.

Patients who participate in this study will be engaging in research and will not be billed for services provided within this protocol.

If subjects will be paid (money, gift certificates, coupons, etc.) to participate in this research project, please note the total dollar amount (or dollar value amount) and distribution plan (one payment, pro-rated payment, paid upon completion, etc) of the payment.

Dollar Amount:

225

Distribution Plan:

Patients will receive a payment voucher in the amount of \$50 for completion of each assessment period (baseline, 1-month, 3-month, & 6 month follow ups). The total amount they may receive is \$200.

A subset of participants who complete treatment and participate in the qualitative interview will receive an additional \$25. The total amount they may receive is \$225.

## **Section M: Genetics**

How would you classify your genetic study?

Discuss the potential for psychological, social, and/or physical harm subsequent to participation in this research. Please discuss, considering the following areas: risks to privacy, confidentiality, insurability, employability, immigration status, paternity status, educational opportunities, or social stigma.

Will subjects be offered any type of genetic education or counseling, and if so, who will provide the education or counseling and under what conditions will it be provided? If there is the possibility that a family's pedigree will be presented or published, please describe how you will protect family member's confidentiality?

## **Section N: Sample Collection**

None

## **Section O: Drug Studies**

Does the research involve the use of ANY drug\* or biologic? (\*A drug is defined as any substance that is used to elicit a pharmacologic or physiologic response whether it is for treatment or diagnostic purposes)

No

Does the research involve the use of ANY gene transfer agent for human gene transfer research?

No

### **O1. Current Drugs**

Is this study placebo-controlled?

No

Will the research involve a radioactive drug that is not approved by the FDA?

No

## **Section P: Device Studies**

Does this research study involve the use of ANY device?

No

## **Section Q: Consent Form(s)**

Transdiagnostic Treatment for Anxiety

Transdiagnostic Treatment for Anxiety Interviews

## **Section R: Advertisements**

### **Mode of Advertising: Other: Flyers, Electronic Messaging Boards, Newsletters**

Exact language of Advertisement:

VETERANS: ARE YOU STRUGGLING WITH ANXIETY?

Symptoms of anxiety may include: constant nervousness, uncontrollable worry, panic attacks, fear or avoidance of situations, people, places, to name a few.

The MEDVAMC is conducting research on a new brief treatment for Veterans with anxiety and related symptoms. The treatment is offered over one weekend or in weekly sessions and includes three follow-up visits. If you are eligible, you may receive this treatment for free and receive compensation for completing assessments over the course of the study.

If you have some of the symptoms listed above and would like more information, please contact the study coordinator at [contact] [name].

Statistical Methods

Specific Aim 1: Examine the effectiveness of iCBT in improving community reintegration and overall quality of life. Community reintegration will be measured using the 3 subscales of the CRIS-CAT: extent of participation, perceived limitations, and satisfaction with participation. Quality of life will be measured by the SF-12 Physical Component Summary (PCS) and Mental Component Summary (MCS) scores. Although our quantitative analyses will be intention-to-treat, we will provide information on the number of and characteristics of any participants who did not receive the treatment as allocated or who did not complete the study. We will tabulate baseline characteristics, such as age, race, gender, disease severity, comorbidities, and psychotropic medications. Based on recommendations of the CONSORT group,⁸¹ we will adjust analyses for variables we have decided *a priori* may be important to control (i.e., depression, period of service [OEF/OIF/OND, Gulf War, and other] concomitant psychotropic medication use, and the primary diagnosis stratification variable). Results from both an intent-to-treat and treatment completer analyses will be compared.

Hypothesis 1a: *iCBT and sCBT will significantly improve community reintegration and quality of life relative to TAU at 3-and 6-month follow-ups.* To compare changes between the iCBT, sCBT, and TAU groups at all time periods in a single regression, we will use a hierarchical mixed-model analysis. Because the number of patients randomized to the 3 groups is not equal, we will test for unequal variances and if necessary, will account for this in our regression models. For outcomes with unequal variances, in the mixed model, we will estimate the variances separately and adjust the degrees of freedom for the unequal variances. The model will contain terms for the intercept, treatment, time period and interaction between time and treatment. *A priori* covariates as well as the stratification variable of anxiety disorders will also be included in the model. A significant time-by-treatment interaction will be followed by pairwise contrasts to determine whether the active interventions differed from TAU and whether the active treatments differed from each other. We will report the p-values and adjust p-values post-hoc using multiple comparisons procedures (e.g., Bonferroni) as recommended in the literature.⁸²

Hypothesis 1b: *iCBT will result in improved reintegration/quality of life measures relative to sCBT at 1-month follow-up.* Only patients in the iCBT and sCBT groups will be used in the analyses. For each outcome, we will run a hierarchical linear regression model using the baseline and 1 month data and with the *a priori* covariates and anxiety disorder stratification variables. Patients will be nested within therapist. The models will contain the 1 month value as the outcome variable and the baseline value of the outcome as an additional covariate. A significant value for the parameter estimate for the intervention will indicate that the iCBT and sCBT groups differed at 1 month.

Specific Aim 2: Examine the effectiveness of iCBT in reducing anxiety/depression symptoms relative to sCBT and TAU. **Hypothesis 2a:** *iCBT and sCBT will significantly reduce anxiety and depression symptoms relative to TAU at 3-and 6- month follow-ups.* The analyses described for hypothesis 1a will be repeated for this hypothesis using the secondary outcomes. Anxiety will be measured using the BAI and depression measured using the BDI-II. **Hypothesis 2b:** *iCBT will result in improved anxiety/depression measures relative to sCBT at 1-month follow-up.* The analyses described for hypothesis 1b will be repeated for this hypothesis using the secondary outcomes.

Specific Aim 3 (Exploratory): Hypothesis 3a: *Compare rates of psychotherapy engagement in iCBT relative to sCBT.* We will use hierarchical logistic regression models to test if the iCBT and sCBT groups differed on treatment engagement (defined as the percentage of randomized patients who participated in 12 or more treatment hours). The outcome will be whether or not

the patient completed 12 or more treatment hours. The a priori variables to be included as independent variables in the treatment engagement model will be selected based on the SOTA Access model described earlier. Items comprising the subscales of geographical, temporal, financial, and cultural barriers will be selected from the PB-SMHS measure for inclusion. The model will also include intervention group and our primary diagnosis stratification variable. To account for clustering, we will nest patients within therapist. **Hypothesis 3b:** Examine heterogeneity of treatment effects on 3- and 6-month outcomes. Because our sample size may not be adequate to substantiate sources of heterogeneity of treatment effects (HTE), exploratory analyses will allow us to describe patterns that can be examined in future larger trials. We will assess HTE on 3-and 6- month effectiveness outcomes through examining potential moderators collected at baseline including demographics, geographic region, co-occurring depression, psychiatric comorbidity, and medication use. Examining the role of potential moderator variables will provide a better understanding of how individuals vary in their response to iCBT and the conditions under which iCBT may be optimal. Following the approach suggested by Kent et al⁸³ for assessing HTE, we will use a multivariable prediction tool to report how relative and absolute risk reduction varies by baseline risk. We will use an internally-developed model from a regression analysis of data from the active treatment arms. Per Brookes et al⁸⁴, we will test the interaction terms in the models as the most statistically robust approach to assessing HTE.

Missing Data for quantitative analyses: To assess impact of missing data, we will conduct sensitivity analyses using tests for missing completely at random and tests for nonrandom missingness using approaches suggested by Molenberghs and Kenward.⁸⁵ These will allow us to evaluate whether the reasons for loss to follow-up at the various time periods are related to the observed values of the outcome variables. We will also plot the data over time to visually assess changes in outcomes from baseline to 3 and 6 months and to indicate whether additional terms are needed in the models to account for nonlinearity over time. *We will also follow recommendations provided by Sterne et al.⁸⁶ regarding multiple imputation methods for missing data in clinical research. In performing our imputation techniques, we will assess non-normality of the data and transform variables as needed to approximate normality before imputation and then transform the imputed values back to the original scale. We will attempt to avoid bias in the imputation analyses by including all variables in the substantive analyses and when computationally feasible, all variables predictive of the missing values and all variables influencing the cause of the missing data, even if they are not of interest in the substantive analysis.*

Initial analyses will be intention-to-treat. We will use the PROC MI in SAS software for multiple imputation of the missing data. The Markov chain Monte Carlo method will be used for imputation if the dataset has arbitrary missing data patterns. PROC MIANALYZE will subsequently be used to combine the results of the analyses of imputation to generate valid statistical inferences. In addition to the analyses of imputed data, we will conduct completer analyses on the observed data. *If the results of the completer analyses and analyses based on imputed values differ, we will look for possible reasons and report this in our publications. Sensitivity analyses will investigate the robustness of the findings to be assumed missing not at random (NMAR).*^{87,88}

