## **Section G: Sample Size/Data Analysis**

### **G1. Sample Size**

How many subjects (or specimens, or charts) will be used in this study?

Local: 335      Worldwide: 335

Please indicate why you chose the sample size proposed:

A total of 335 participants will be recruited for this study: 252 Veterans will be recruited to participate in the RCT; 40 Veterans who participated in iCBT and their family members (up to 40) will be invited to participate in the qualitative interview.

For the RCT, a total of 252 patients will be randomized across the 3 arms (95 to iCBT, 95 to sCBT, and 62 to TAU) to have 80% power to detect differences among groups in the primary outcomes. A recent meta-analysis of transdiagnostic treatment for anxiety demonstrated a medium effect size ( $g=.69$ ) on quality of life outcomes. Based on these findings, we are using a more conservative effect size of 0.50 to calculate the sample size that will need to be recruited and randomized to draw conclusions. We will use unequal randomization to the active intervention arms and to treatment as usual to reduce unnecessary recruitment. We also inflated the sample size to account for intraclass correlations among patients and for attrition and loss to follow-up in order to obtain the number that must be recruited for the study. The recruited sample size of 95 for iCBT and 95 for sCBT, assuming 20% attrition at 1 month and accounting for clustering of patients within therapists, will result in 49 patients per group for analysis. For our primary analyses, this sample size will have 80% power to detect a medium effect size of .57 using a two-group t-test with  $\alpha=.05$  two-sided significance level.

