### **G2. Data Analysis**

Provide a description of your plan for data analysis. State the types of comparisons you plan (e.g. comparison of means, comparison of proportions, regressions, analysis of variance). Which is the PRIMARY comparison/analysis? How will the analyses proposed relate to the primary purposes of your study?

For our primary analyses, we will compare changes between the iCBT, sCBT, and TAU groups at all time periods in a single regression using a hierarchical mixed-model analysis. Because the number of patients randomized to the 3 groups is not equal, we will test for unequal variances and if necessary, will account for this in our regression models. For outcomes with unequal variances, in the mixed model, we will estimate the variances separately and adjust the degrees of freedom for the unequal variances. A priori covariates will also be included in the model. A significant time-by-treatment interaction will be followed by pairwise contrasts to determine whether the active interventions differed from TAU and whether the active treatments differed from each other. We will report the p-values and adjust p-values post-hoc using multiple comparisons procedures (e.g., Bonferroni) as recommended in the literature. For secondary analyses, we will run hierarchical linear regression models for each outcome using the baseline and 1 month data and with the a priori covariates. Hierarchical logistic regression models will be used to test differences in treatment engagement across conditions.

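### Arm-specific variances hinge on a preliminary test with no stated criterion, so active-versus-TAU standard errors can be modestly off in either direction

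*SAP*

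**What the plan says.** The SAP (Specific Aim 1, Hypothesis 1a) fits one hierarchical mixed model to all three arms and all time points. On variances it says "we will test for unequal variances and if necessary, will account for this in our regression models". For outcomes judged unequal, "in the mixed model, we will estimate the variances separately and adjust the degrees of freedom".

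Protocol G2 gives the same two-stage rule under the primary analyses: "Because the number of patients randomized to the 3 groups is not equal, we will test for unequal variances", followed by "For outcomes with unequal variances, in the mixed model, we will estimate the variances separately". For the BAI and BDI-II under Hypothesis 2a, the SAP states "The analyses described for hypothesis 1a will be repeated for this hypothesis using the secondary outcomes", so the rule carries over.

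Neither document names the test, the cut-off, or the level of the model at which variances are compared. Neither plans a robust or unconditional arm-specific variance. Allocation is "95 to iCBT, 95 to sCBT, and 62 to TAU" (Protocol G1).

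**The concern.** The choice of error model is left to a data-driven step, taken outcome by outcome: five primary scores (three CRIS-CAT subscales, PCS and MCS) and two secondary ones. A variance test in arms of this size has limited power against moderate differences, so the pooled model can be kept when it is wrong.

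Unequal allocation makes this matter for the contrasts with TAU. The pooled variance is weighted toward the two larger active arms, while the sampling variance of the contrast is weighted toward the smaller TAU arm. If TAU is more variable, the pooled standard error is too small and the test is liberal. If TAU is less variable, the standard error is too large and the test is conservative.

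A different spread in TAU is possible: Protocol F2 describes it as anything from medication visits alone to disorder-specific evidence-based therapy. The documents do not indicate the direction or size. At stake is the calibration of p-values and intervals for iCBT versus TAU and sCBT versus TAU.

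**Working it through.** **Inputs from Protocol G1.** Randomized 95/95/62; two-sided alpha .05; for the active arms, "assuming 20% attrition at 1 month and accounting for clustering of patients within therapists, will result in 49 patients per group for analysis".
- 95 × 0.8 = 76 and 62 × 0.8 = 49.6, about 50. Applying the 1-month attrition figure to TAU, and to later visits, is an assumption.
- Implied design effect 76/49 = 1.55. Applied to TAU as well (an assumption), 49.6/1.55 = 32.
- Sizes examined: 95/95/62, 76/76/50 and 49/49/32.

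**Assumed, not in the documents.** Ratio r = TAU SD / active SD, with the two active arms equal; normal outcomes; Brown-Forsythe pretest at .05.

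**The plan's own figure.** Protocol G1 claims "80% power to detect a medium effect size of .57 using a two-group t-test" with 49 per group. Normal approximation: Φ(0.57 × √(49/2) − 1.96) = Φ(2.82 − 1.96) = 80.5%. The exact noncentral t gives 79.8%. The figure reproduces. It describes iCBT versus sCBT, does not involve TAU, and is unaffected by this point.

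**Standard error if pooling is kept.** With active SD = 1,

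pooled variance = [(n₁−1) + (n₂−1) + (n_T−1)r²] / (N−3)

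SE ratio = √{ pooled variance × (1/n₁ + 1/n_T) / (1/n₁ + r²/n_T) }

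At 76/76/50:
- r = 1.25: pooled variance = (150 + 49 × 1.5625)/199 = 1.1385. SE ratio = √(1.1385 × 0.03316 / 0.04441) = 0.92, about 8% too small.
- r = 0.75: pooled variance = (150 + 49 × 0.5625)/199 = 0.8923. SE ratio = √(0.8923 × 0.03316 / 0.02441) = 1.10, about 10% too large.
- By the same formula, 0.90 at r = 1.33 and 0.86 at r = 1.5.

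**Simulation.** 20,000 null trials per setting, one time point. If the pretest rejects, a Welch contrast is used; otherwise a contrast with variance pooled over three arms. Monte Carlo standard error near 5% is √(.05 × .95/20,000) = 0.15 points.

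Pretest detection rate:

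| r | 95/95/62 | 76/76/50 | 49/49/32 |
|---|---|---|---|
| 0.75 | 57% | 46% | 28% |
| 0.80 | 37% | 29% | 18% |
| 1.25 | 42% | 34% | 22% |
| 1.33 | 63% | 53% | 35% |
| 1.5 | 91% | 83% | 62% |
| 2.0 | 100% | 99.9% | 98% |

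Type I error of one active-versus-TAU contrast (two-stage rule / arm-specific variance always):

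| r | 95/95/62 | 76/76/50 | 49/49/32 |
|---|---|---|---|
| 0.75 | 4.2 / 4.8% | 4.4 / 5.1% | 3.8 / 5.0% |
| 0.80 | 4.3 / 5.1% | 4.4 / 5.3% | 3.9 / 5.0% |
| 1.0 | 5.0 / 5.0% | 5.1 / 5.1% | 4.8 / 4.9% |
| 1.25 | 5.9 / 4.9% | 5.8 / 4.8% | 6.4 / 5.0% |
| 1.33 | 5.9 / 5.1% | 6.1 / 5.2% | 6.4 / 5.0% |
| 1.5 | 5.4 / 5.2% | 5.3 / 4.9% | 6.2 / 5.0% |
| 2.0 | 5.0 / 5.0% | 5.0 / 5.0% | 5.1 / 5.0% |

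A separate run at 76/76/50 gave 4.1% at r = 0.77 and 6.4% at r = 1.3. Among trials where the pretest did not reject, so that pooling was kept, type I error was 3.1% to 3.5% at r = 0.75, 7.0% to 7.1% at r = 1.25 and 8.0% to 8.4% at r = 1.33.

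**The case against.** The plan does not ignore unequal variances. It already names the right model as a fallback, and what is disputed is the default. That is correct, and it is why the point is minor.

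The size depends on a test the documents do not name. At 76/76/50 and r = 1.3, 12,000 null trials gave 6.2% with Brown-Forsythe at .05, 5.8% with Bartlett at .05 and 5.1% with Bartlett at .20. A lenient criterion would nearly remove the problem, but none is stated.

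The planned procedure also tests pairwise contrasts only after a significant interaction, and then adjusts p-values. With a one-time-point omnibus gate and Bonferroni over three contrasts, the chance of any false pairwise claim under the global null was 3.7% (r = 0.77), 4.2% (1.0), 4.5% (1.2) and 4.8% (1.3), never above 5%. A reader might infer that the trial's false-positive rate is 6.4%; the documents do not support that. What stands is the relative distortion for one contrast (2.4% at the high end against 1.6% at equal SDs) and the effect on confidence intervals, which the gate does not protect.

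Two further inferences fail. The plan's reason for testing, the unequal arm sizes, need not mean that it takes unequal sizes as evidence of unequal variances; it reads naturally as recognizing that pooling is then less safe. And group delivery in the active arms does not by itself imply a different residual variance: it creates within-group correlation, which arm-specific residual variances do not model.

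Finally, the complete-data simulation does not cover the planned multiple imputation. Imputation not run by arm assumes a common covariance and would pull the arms' variances together, so the fix has to address it.

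**Conclusion.** The point holds as a minor one. The two-stage rule is in both documents, its criterion is unstated, and 95/95/62 allocation leaves the TAU contrasts exposed. Standard errors **can** be off, by roughly 8% to 10% at ratios of 0.75 to 0.80 and 1.25 to 1.33, when variances truly differ by that much and the test misses it. Over those ratios and the three sizes, the assumed test misses about 37% to 82% of the time. The resulting type I error for a single contrast is about 4% to 6.4%.

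These figures rest on assumed SD ratios, an assumed Brown-Forsythe test at .05, and one unadjusted, ungated contrast at one time point without covariates or clustering. A reader might infer that the intervals are wrong as planned, or that the test generally fails. Neither is supported: no arm SDs are given, and at 76/76/50 a 1.5-fold difference is detected 83% of the time (62% at 49/49/32).

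**What to change.** In the SAP under Hypothesis 1a, and in Protocol G2, delete the variance pretest. Pre-specify arm-specific residual variances (for example a REPEATED statement with GROUP=arm) with Satterthwaite or Kenward-Roger degrees of freedom for every Hypothesis 1a and 2a outcome, alongside the planned random effects. Where multiple imputation is used, run PROC MI by arm and combine with the planned PROC MIANALYZE rules using small-sample degrees of freedom.

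The cost is a short text change and a slight loss of degrees of freedom if variances are in fact equal. In the simulations, always using arm-specific variances gave type I error of 4.6% to 5.3% throughout and about 5% at equal variances. Sample size, conduct and data collection do not change, and one post-data choice per outcome is removed.

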## **Section F: Design/Procedure**

### **F1. Design**

Select one category that most adequately describes your research:

c) Pilot

Discuss the research design including but not limited to such issues as: probability of group assignment, potential for subject to be randomized to placebo group, use of control subjects, etc.

The clinical trial will compare the effectiveness of iCBT to standard CBT (sCBT) and treatment as usual (TAU). A total of 252 Veterans from all war eras will be recruited who have at least one of the following disorders: PTSD, panic disorder (PD), social anxiety disorder (SAD) and generalized anxiety disorder (GAD). Veterans with or without co-occurring depression will be included. Participants will be randomized to iCBT, sCBT, or TAU. The study design uses unequal randomization to the active intervention arms and to treatment as usual to reduce unnecessary recruitment. Thus, the percent chance that participants will be randomized to one of the three conditions are: 37% iCBT, 37% sCBT, and 24%TAU. Participants in iCBT will receive treatment over one weekend (16 total session hours); those in sCBT will receive the same treatment weekly, over 12 weeks (16 total session hours); and those assigned to TAU will receive routine clinical care. Assessments will be completed at four time points: baseline, 1-month, 3-months, and 6-months.

This protocol should be considered minimal risk because the likelihood and degree of discomfort anticipated in this intervention are lower than what people would encounter in daily life. This is a non-invasive behavioral intervention that is designed as a two-day workshop to teach participants about anxiety and provide them with opportunities to practice examining and adjusting their thoughts based on evidence. Participants have the benefit of having trained therapists available to guide and help them engage in these exercises. The workshop is similar to other classes and seminars people may attend in daily life. The room is set up as a classroom with individual desks and chairs for participants. Breaks are scheduled throughout the day, and participants are informed that they may take a break whenever they need.

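### The primary H1a mixed model, repeated for H2a, leaves some baseline precision unused; a common baseline mean and a matching joint test would recover it at no cost in data

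*SAP*

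**What the plan says.** Protocol G2 identifies the three-arm longitudinal model as primary: "For our primary analyses, we will compare changes between the iCBT, sCBT, and TAU groups at all time periods in a single regression". SAP Hypothesis 1a states the target, "iCBT and sCBT will significantly improve community reintegration and quality of life relative to TAU at 3-and 6-month follow-ups", and lists the fixed effects: "The model will contain terms for the intercept, treatment, time period and interaction between time and treatment". To these it adds covariates chosen in advance, given under Specific Aim 1 as a closed list: "depression, period of service [OEF/OIF/OND, Gulf War, and other] concomitant psychotropic medication use, and the primary diagnosis stratification variable". The outcome's own baseline value is not on that list, and nothing constrains the arms to share a baseline mean.

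The arm comparisons depend on a preliminary test: "A significant time-by-treatment interaction will be followed by pairwise contrasts to determine whether the active interventions differed from TAU". Hypothesis 2a inherits all of this for the BAI and BDI-II: "The analyses described for hypothesis 1a will be repeated for this hypothesis using the secondary outcomes".

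Hypothesis 1b, the two-arm comparison at 1 month, is built differently: "The models will contain the 1 month value as the outcome variable and the baseline value of the outcome as an additional covariate".

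Protocol F1 fixes the visits: "Assessments will be completed at four time points: baseline, 1-month, 3-months, and 6-months". The CRIS-CAT, SF-12, BAI and BDI-II are not among the instruments that the Assessment Battery section restricts to baseline, so each has a baseline and three follow-up values in every arm.

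**The concern.** Patients are randomised, and the baseline evaluation precedes treatment, so the arms have the same expected baseline score. A model with a free treatment term plus time-by-treatment terms estimates a separate baseline mean for each arm. A change-from-baseline contrast then subtracts a noisy baseline difference whose true value is zero. Imposing a common baseline mean, or adjusting for the baseline outcome, avoids paying for that noise.

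The listed covariates do not do this job. They enter as main effects that are constant over time, so with complete data they cancel from a change contrast and leave its variance as it was. If depression means baseline BDI-II (the SAP does not name the measure), the same applies to change contrasts for the BDI-II outcome in H2a.

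At stake are the width of the confidence intervals for the active-versus-TAU estimates at 3 and 6 months, and the chance of passing the interaction test that the SAP requires before those estimates are compared.

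**Working it through.** **The plan's own figure.** Protocol G1 gives 95 per CBT arm, 20% attrition at 1 month and 49 per group for analysis after clustering, with 80% power for an effect of .57 (two-sided .05, two-group t-test). The noncentral t with 49 v 49 gives 79.8%, so the figure reproduces. Also 95 × 0.8 = 76, and 76/49 = 1.55 is the implied design effect. For TAU, 62 × 0.8 = 49.6.

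**Assumed inputs.** The correlation ρ between baseline and follow-up is not in the documents; 0.3, 0.5 and 0.7 are used. Data are complete, and follow-up variance is set to 1.

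**Standard error of a change contrast, no clustering.** Let s = 1/n₁ + 1/n₂, with equal variances at baseline and follow-up.
- As written: 2(1−ρ)s, that is 1.40s, 1.00s, 0.60s.
- Baseline-adjusted or common baseline mean: (1−ρ²)s, that is 0.91s, 0.75s, 0.51s.
- The ratio is (1+ρ)/2 = 0.65, 0.75, 0.85. Variance falls by 35, 25, 15% and the SE by 19, 13, 8%.

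A generalised least squares calculation with three arms, four visits and compound symmetry gives the same factors.

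**Active versus TAU with clustering.** Assume the whole fall from 76 to 49 is therapist variance that baseline does not predict, that it persists at 3 and 6 months, and that it affects only the CBT arm. Then s = 1/95 + 1/62 = 0.02666, and 0.551/95 = 0.0058 is added to both variances.

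| ρ | As written | Adjusted | SE reduction |
|---|---|---|---|
| 0.3 | 0.0431 | 0.0301 | 16–17% (0.165) |
| 0.5 | 0.0325 | 0.0258 | 11% |
| 0.7 | 0.0218 | 0.0194 | 6% |

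**Unequal variances, no clustering.** If baseline variance is k times follow-up variance, the change contrast has variance (1 + k − 2ρ√k)s, while the adjusted one stays at (1−ρ²)s.
- k = 0.7: 1.198, 0.863, 0.529 against 0.91, 0.75, 0.51. The SE falls by 13, 7, 2%.
- k = 0.5: 1.076, 0.793, 0.510 against the same. The SE falls by 8, 3, 0%.

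A baseline variance above the follow-up variance would raise the gain.

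**The interaction gate.** Inputs: 76/76/50 patients, compound symmetry, no clustering, noncentral F with 6 and 199 degrees of freedom, α = .05. The effect is 0.50 SD, one of the two effect sizes in Protocol G1, in both CBT arms at every follow-up, except that sCBT has 0.25 SD at 1 month. That exception is an assumption, made because the sCBT course lasts 12 weeks and H1b expects iCBT to be ahead at 1 month.

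| Test | ρ = 0.3 | ρ = 0.5 | ρ = 0.7 |
|---|---|---|---|
| Time-by-treatment as written (6 df) | 70% | 86% | 98% |
| Joint test of baseline-adjusted post-baseline effects (6 df) | 95% | 97% | 100% |
| Interaction among post-baseline visits only (4 df) | 23% | 31% | 50% |

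The gap between the first two rows widens if the effect is constant over follow-up. It narrows if sCBT has no effect yet at 1 month (92, 98, 100% against 99, 100, 100%).

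**The case against.** The strongest reply is that nothing here is wrong. A longitudinal model with baseline in the response and treatment, time and their interaction is standard and valid, and H1b's baseline covariate is the natural form for a two-arm analysis with one follow-up. That stands. A reader might infer from the contrast with H1b that the SAP contradicts itself, that the primary estimates are biased, or that the power statement fails. The documents support none of these: the two models answer different questions, randomisation protects both, and the stated power reproduces.

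A reader might also infer that the scale of the H1a contrasts is wholly open. The contrast sentence does not state it, but both documents describe the model as comparing changes, and the SAP's missing-data section refers to change from baseline to 3 and 6 months. Change from baseline is the natural reading. Gains computed for simple differences at a visit should therefore carry no weight.

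The size is uncertain, and that stands too. The correlation is assumed, and entry is limited to Q-LES-Q-SF scores of 42 or lower, a related quality-of-life measure. That could narrow the baseline spread of the outcomes and shrink the gain. Nor should a clustered gain be quoted for iCBT versus sCBT: Protocol F2 has the interventionists trained to deliver both formats, so shared therapist effects would largely cancel.

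Multiple imputation does not answer the point. It fills in missing values; it does not change how the analysis model uses observed baselines.

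**Conclusion.** The point holds as a loss of efficiency only. For 0 < ρ < 1, with equal variances, 1−ρ² is smaller than 2(1−ρ); with unequal variances the adjusted variance is, in large samples, never larger than that of the change contrast. Some precision in the primary H1a estimates and their H2a repeats is therefore normally left unused. With equal variances and ρ of 0.3 to 0.7, the unused part is 8–19% of the SE without clustering and about 6–16% for active versus TAU under the implied design effect. It could be near zero if baseline scores are much less variable than follow-up scores. The gate is where the loss may matter most: at low ρ, in the scenario shown, the required interaction test passes about 70% of the time where a baseline-adjusted joint test would pass about 95%. At ρ = 0.7 the two barely differ. The change is worth making because it is nearly free, not because the present analysis is unsound.

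**What to change.** In H1a and H2a, keep baseline in the outcome vector with one common mean across arms, treatment-by-time terms at 1, 3 and 6 months, and an unstructured covariance over visits. Alternatively, model the three follow-up values with the baseline outcome and its interaction with time as covariates.

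In the same revision, define the gate as the joint test that every post-baseline treatment effect is zero, and name the baseline-adjusted between-arm differences at 3 and 6 months as the contrasts.

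The two changes must go together. If only follow-up visits are modelled and the time-by-treatment interaction stays as the gate, the test asks whether the effect varies between follow-ups, and power falls to the last row of the gate table.

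The cost is SAP wording and model code. No new data, visits or participants are needed.
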